## 2. INTRODUCTION

The purpose of this study is to assess the efficacy and safety of human FcRn blocking therapy with efgartigimod compared to placebo, in participants with pSS.

# 2.1. Study Rationale

For many decades, the clinical needs for pSS have been left unresolved because of the rareness of the disease and the complexity of the underlying pathogenic mechanisms. It has become clear that B-cell activation and development of autoantibodies play an important role in pSS.

Efgartigimod is a first-in-class antibody fragment that binds to the FcRn. This binding prevents FcRn from recycling IgG and leads to a reduction in circulating disease-causing autoantibodies. Efgartigimod is being clinically developed in autoimmune diseases mediated by pathogenic IgG autoantibodies after approval by the United States FDA and Japan's PMDA for use in adult patients with AChR-Ab seropositive gMG.

Efgartigimod may be a viable treatment option for individuals diagnosed with pSS because it has been shown to reduce IgG levels, including IgG autoantibodies, that may underlie some of the autoimmune disease manifestations in these participants. Therefore, the reduction of autoantibodies may successfully reduce disease activity and symptoms in pSS participants.

# 2.2. Background

pSS is a chronic, progressive autoimmune disease of unknown etiology, typically characterized by an autoimmune exocrinopathy. Along with symptoms of excessive dryness, manifestations include profound fatigue, chronic pain, extraglandular organ system involvement, and increased risk of lymphomas. A hallmark of pSS is B-cell hyperactivity, causing a vicious cycle of immune activation through cytokine production, antigen presentation, and autoantibody secretion, potentially causing tissue damage. Currently, no immunomodulatory treatment is available for pSS.

This study aims to evaluate the effect of efgartigimod, an FcRn antagonist that can rapidly reduce IgG, including pathogenic antibodies. Efgartigimod has the potential to successfully treat pSS and improve disease manifestations by the reduction of IgG autoantibodies in pSS.

A detailed description of the chemistry, pharmacology, efficacy, and safety of efgartigimod is provided in the current IB.

#### 2.3. Benefit/Risk Assessment

More detailed information about the known and expected benefits and risks and reasonably expected AEs of efgartigimod is provided in the current IB.

#### 2.3.1. Risk Assessment

Overall, available data confirm that efgartigimod IV has been well tolerated across studies in different indications and has an acceptable safety profile.

Potential clinically significant risk	Summary of data/ rationale for risk	Mitigation strategy
Serious infection	Efgartigimod reduces IgG levels, potentially hindering immune response and increasing the	Exclude participants with clinically significant uncontrolled infections (Section 5.2).
	infection risk.	Monitor for infections, considered an adverse event of special interest (AESI; Section 8.4.6), and temporarily interrupt IMP dosing as specified in Section 7.1.
Infusion-related reactions (IRR)	All therapeutic proteins have the potential to elicit immune responses, potentially resulting in hypersensitivity or allergic reactions such as rash, urticaria, angioedema, serum sickness, and anaphylactoid or anaphylactic reactions.	As with any IV infusion, the potential exists for IRR, which may occur during or within 48 hours after infusion.  Pretreatment to prevent an IRR is not required. IMP will be administered by a healthcare professional.

## 2.3.2. Benefit Assessment

Efgartigimod has been investigated in nonclinical studies, phase 1 clinical pharmacology studies in healthy participants, and phase 2/3 clinical studies in participants with IgG-driven autoimmune diseases, including gMG, primary ITP, CIDP, and pemphigus.

In clinical studies, efgartigimod effectively reduces IgG antibody levels, including pathogenic autoantibodies. The efficacy of efgartigimod to improve clinical outcomes in gMG and reduce pathogenic autoantibodies was confirmed in a pivotal phase 3 study in participants with gMG (ARGX-113-1704). Clinical benefit was also observed in phase 2 studies in primary ITP (ARGX-113-1603) and pemphigus (ARGX-113-1701), in which pathogenic autoantibodies underlie the disease pathology (refer to current efgartigimod IB). Available clinical data support the clinical benefit of efgartigimod for reducing pathogenic IgG autoantibodies, which may mitigate autoimmune dysfunction and improve symptoms, as well as the ability to function, in participants with pSS.

#### 2.3.3. Overall Benefit-Risk Conclusion

The potential risks associated with efgartigimod are justified by the anticipated benefits afforded to participants with pSS in this study and considering the measures implemented to minimize risks. The favorable balance between risks and anticipated efficacy/benefit supports the use of efgartigimod in the clinical development for pSS.

More detailed information about the known and expected benefits and risks of efgartigimod and reasonably expected AEs can be found in the current IB.

# 3. OBJECTIVES, ENDPOINTS, AND ESTIMANDS

Table 1: Study ARGX-113-2106 Objectives and Endpoints

Objectives	Endpoints
Primary	
To evaluate the effect of efgartigimod IV compared to placebo on CRESS	
 
Proportion of CRESS responders on ≥ 3 of 5 items at week 24 (refer to Section 8.2.1). The 5 items are:         
 
Systemic disease activity: clinESSDAI
 
Patient-reported symptoms: ESSPRI
 
Tear gland function: Schirmer's test and OSS
 
Salivary gland function: UWSF rate and SGUS
 
Serology (serum IgG and/or RF)
 
 
 

Secondary	serology (serum 150 and of 14)
To evaluate the effect of efgartigimod IV compared to placebo on the histology of the parotid gland (selected sites only)	
 
Change in the relative counts of lymphocytic infiltrate (stained for CD45) at week 24
 
Change in B/B+T cell ratio at week 24
 

To evaluate the safety of efgartigimod IV compared to placebo in participants with pSS	
 
Incidence and severity of TEAEs, AESIs, and SAEs by SOC and PT
 
Changes in vital sign measurements, ECG results, and clinical laboratory safety evaluations
 

To evaluate the effect of efgartigimod IV compared to placebo on clinical efficacy parameters	
 
Proportion of participants with minimal clinically important improvement in ESSDAI: improvement of ≥ 3 points in ESSDAI score at week 24
 
Proportion of participants with low disease activity: ESSDAI score of < 5 at week 24
 
Proportion of participants with minimal clinically important improvement in clinESSDAI: improvement of ≥ 3 points in clinESSDAI score at week 24
 
Proportion of participants with low disease activity: clinESSDAI score of < 5 at week 24
 
Proportion of participants with minimal clinically important improvement in ESSPRI: decrease of 1 point or ≥ 15% at week 24
 
Change in ESSDAI score at week 24
 
Change in clinESSDAI score at week 24
 
Change in ESSPRI score at week 24
 

To evaluate the effect of efgartigimod IV compared to placebo on STAR	• Proportion of participants with STAR score of ≥ 5 at week 24

30

Objectives	Endpoints
To evaluate the PK of efgartigimod IV	Efgartigimod serum concentration-time profile
To evaluate the PD of efgartigimod IV	Values, changes from baseline, and percent reduction from baseline in total IgG levels in serum      Values, changes from baseline, and percent reduction from baseline.
	
 
Values, changes from baseline, and percent reduction from baseline in autoantibodies in serum:
 
Anti-Ro/ SS-A
 

	– Anti-La/ SS-B
To evaluate the immunogenicity of efgartigimod IV	Incidence and prevalence of ADA against efgartigimod in serum
Exploratory	
•	
	•
	•
	•
	•
•	•
	•
	•
	•
	•

Objectives	Endpoints
•	

Note: Estimands are not defined for this phase 2 study.

ADA=antidrug antibody; AESI=adverse event of special interest;
clinESSDAI=clinical EULAR Sjögren's syndrome disease activity
index; CRESS=Composite of Relevant Endpoints for Sjögren's Syndrome; ECG=electrocardiogram;
ESSDAI=EULAR Sjögren's syndrome disease activity index; ESSPRI=EULAR Sjögren's Syndrome Patient
Reported Index: IgG=immunoglobulin G;
; IV=intravenous; ; OSS=ocular staining score;
; PD=pharmacodynamic(s); PK=pharmacokinetic(s); pSS=primary
Sjögren's syndrome; PT=preferred term; SAE=serious adverse event; SGUS=salivary gland ultrasonography;
SOC=system organ class; SS-A=Sjögren's syndrome-related antigen A; SS-B=Sjögren's syndrome-related antigen
B; STAR=Sjögren's Tool for Assessing Response; SWSF=stimulated whole salivary flow;
TEAE=treatment-emergent adverse event; UWSF=unstimulated whole salivary flow;

## 4. STUDY DESIGN

# 4.1. Overall Design

This is a randomized, double-blinded, placebo-controlled, phase 2, multicenter study.

For participants not enrolling in the OLE study, the study duration is approximately 36 weeks, spanning the following study periods:

• Screening:  $\leq 4$  weeks

• Treatment: 24 weeks

• Follow-up: 56 days

For participants enrolling in the OLE study, the study duration is approximately 28 weeks, spanning the following study periods:

• Screening:  $\leq 4$  weeks

• Treatment: 24 weeks

The study population includes adult participants with pSS, per ACR/EULAR 2016 classification criteria, with at least a moderate level of systemic disease activity (ESSDAI  $\geq$  5).

Participants will be randomized to receive efgartigimed IV 10 mg/kg or placebo in a 2:1 ratio, respectively.

All participants will receive efgartigimod IV 10 mg/kg or placebo once weekly for 24 weeks during the treatment period.

IMP will be administered as an approximately 1-hour IV infusion by site staff or a home nurse. The final dose will be administered at week 23.

At week 24, eligible participants may roll over to the single-arm OLE study.

# 4.2. Scientific Rationale for Study Design

pSS is characterized by mononuclear inflammatory infiltrates and IgG plasma cells in salivary and lacrimal glands that lead to irreversible destruction of the glandular tissue and is accompanied by a sensation of dryness of mouth and eyes. B cells play a central role in the immunopathogenesis and exhibit signs of hyperactivity. In addition, autoantibodies can create immune complexes that maintain and amplify the production of IFN alpha. This combination results in a cycle of immune activation that leads to tissue damage. Currently, no immunomodulatory treatment is available for pSS. In this study, we aim to evaluate the effect of efgartigimod, an FcRn antagonist that can rapidly reduce IgG, including pathogenic antibodies. Efgartigimod has the potential to successfully treat pSS and improve disease manifestations by the reduction of IgG autoantibodies and immune complexes in pSS.

This study aims to investigate the efficacy and safety of efgartigimod compared to placebo in participants with pSS. The study design is randomized, double-blinded, and placebo-controlled to evaluate the effect of efgartigimod administered as an IV infusion compared to placebo. The study consists of a treatment period when all participants will receive weekly IV infusions for

24 weeks. The comparison to placebo is justified because there are no standardized approved therapies for pSS.

The primary endpoint is the effect of efgartigimod IV compared to placebo on CRESS (Section 8.2.1). The CRESS composite measures systemic disease activity, patient-reported symptoms, tear gland function, salivary gland function, and serology, developed to assess treatment efficacy in participants with pSS. CRESS has been selected as the primary efficacy endpoint because a composite is presumed to be more appropriate in demonstrating drug efficacy compared to an endpoint that reports on a single aspect of this heterogeneous disease. In randomized controlled studies that previously showed negative primary endpoint results using ESSDAI, post hoc analysis of the study data using CRESS resulted in higher response rates in participants treated with efgartigimod, compared to those given placebo. Use of CRESS also resulted in decreased placebo response rates compared with the use of the ESSDAI minimal clinically important improvement, which is essential to demonstrating treatment efficacy.

The secondary endpoints complement the primary endpoint and provide additional information on efficacy (ESSDAI, clinESSDAI, ESSPRI, STAR [Section 8.2]), histology, safety, PK, PD, and immunogenicity. The totality of data from all endpoints used in the study will be utilized to determine treatment response in this population.

#### 4.3. Justification for Dose

Weekly doses of efgartigimod IV 10 mg/kg will be administered to attain a maximal total IgG reduction (PD effect), thereby ensuring maximal clinical response on the efficacy outcomes.

Because the hypothesis for treating pSS with efgartigimed is to reduce the pathogenic autoreactive IgG, the selected dose and frequency target a nearly maximal PD effect (ie, reduction of pathogenic IgGs). Considering the chronic nature of pSS, the dosing regimen of weekly IV administration reflects the need for chronic treatment to maintain pathogenic IgG autoantibody suppression and symptom reduction.

The cumulative data from a phase 1 study in healthy adult participants; phase 2 studies in participants with gMG, ITP, and pemphigus; phase 3 studies in participants with gMG and ITP; and PK/PD modeling results showed that weekly infusions of efgartigimod IV 10 mg/kg demonstrated an approximately 70% reduction in IgG, including pathogenic autoantibodies. Maximal IgG reduction was associated with clinical efficacy observed in gMG, ITP, and pemphigus studies. Furthermore, this dose has been safe and well tolerated in all study populations and has demonstrated similar PK and PD profiles across indications. Accordingly, the 10 mg/kg weekly IV dose regimen was selected for this study.

# 4.4. End-of-Study Definition

The end-of-study is defined as the date of the last participant's last visit.

A participant will have completed the study if the treatment period (or follow-up period, if applicable) has been completed.

• Participants rolling over to the OLE study will have completed this study at week 24

• Participants not rolling over to the OLE study will have completed this study after the SFV or EDV. If a participant continued in the study after discontinuing IMP, this will be week 24 or at the SFV (if permanent IMP discontinuation is < 56 days from week 24).

## 5. STUDY POPULATION

Prospective approvals of protocol deviations to enrollment criteria, also known as protocol waivers or exemptions, are not permitted.

## 5.1. Inclusion Criteria

Participants are eligible to be included in the study only if all of the following criteria apply:

- 1. Is at least the legal age of consent for clinical trials when signing the informed consent form
- 2. Is capable of providing signed informed consent, as described in Section 10.1.3, and complying with protocol requirements
- 3. Agrees to use contraceptive measures consistent with local regulations and the following:
  - a. Male participants: refer to Section 10.4.2.2
  - b. WOCBP (defined in Section 10.4.1) must have a negative serum pregnancy test at screening and a negative urine pregnancy test at baseline before receiving IMP. Contraceptive requirements are provided in Section 10.4.
- 4. Meets the following criteria at screening:
  - a. ACR/EULAR 2016 pSS who met criteria ≤ 7 years before screening
  - b. ESSDAI  $\geq 5$
  - c. Anti-Ro/SS-A positive
  - d. Residual salivary flow (UWSF rate > 0 and/or SWSF rate > 0.10)

## 5.2. Exclusion Criteria

Participants will be excluded from the study if any of the following criteria apply:

- 1. Known autoimmune disease or any medical condition that, in the investigator's judgment, would interfere with an accurate assessment of clinical symptoms of pSS or puts the participant at undue risk
- 2. History of malignancy unless considered cured by adequate treatment with no evidence of recurrence for  $\geq 3$  years before the first administration of IMP. Adequately treated participants with the following cancers may be included at any time:
  - a. Basal cell or squamous cell skin cancer
  - b. Carcinoma in situ of the cervix
  - c. Carcinoma in situ of the breast
  - d. Incidental histological finding of prostate cancer (TNM stage T1a or T1b)
- 3. Clinically significant uncontrolled active acute or chronic bacterial, viral, or fungal infection
- 4. Positive serum test at screening for an active infection with any of the following:
  - a. HBV that is indicative of an acute or chronic infection, unless associated with a negative HBsAg or negative HBV DNA test
  - b. HCV based on HCV antibody assay unless a negative RNA test is available

- c. HIV based on test results of a CD4 count of < 200 cells/mm^3 that are associated with an AIDS-defining condition
- d. HIV based on test results of a CD4 count of ≥200 cells/mm³ not adequately treated with antiviral therapy
- 5. Clinically significant disease, recent major surgery (within 3 months of screening), or intention to have surgery during the study; or any other medical condition that, in the investigator's opinion, would confound the results of the study or put the participant at undue risk
- 6. Current participation in another interventional clinical study
- 7. Known hypersensitivity to IMP or 1 of its excipients
- 8. History (within 12 months of screening) of current alcohol, drug, or medication abuse as assessed by the investigator
- 9. Pregnant or lactating state or intention to become pregnant during the study
- 10. Previously participation in an efgartigimod clinical study and treatment with  $\geq 1$  dose of IMP
- 11. Total IgG of < 4 g/L at screening
- 12. Secondary Sjögren's syndrome overlap syndromes where another confirmed autoimmune rheumatic or systemic inflammatory condition (eg, rheumatoid arthritis, systemic lupus erythematosus, scleroderma, inflammatory bowel disease) is the primary diagnosis
- 13. Positive SARS-CoV-2 PCR test at screening
- 14. Any severe systemic pSS manifestation that may put the participant at undue risk based on the investigator's opinion

Note: Medications cited in exclusion criteria 15-22 are also prohibited during the screening period.

- 15. IVIg, SCIg, or PLEX  $\leq$  12 weeks before screening
- 16. Live or live-attenuated vaccine  $\leq 4$  weeks before screening
- 17. Pilocarpine and/or any other pharmacological stimulant for salivary and lacrimal glands that is not at a stable dose in the 4 weeks prior to screening or is started≤ 4 weeks from screening
- 18. Anticholinergic agents which are not at a stable dose weeks prior to screening or during screening
- 19. Corticosteroids:
  - a. Intramuscular or IV corticosteroids ≤ weeks from screening
  - b. Oral corticosteroids if above 10 mg, or if not at a stable dose ≤ weeks from screening
  - c. ≤ weeks from screeningd. Use of is prohibited

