# **10.2.** Appendix 2: Clinical Laboratory Tests

The tests listed in Table 6 will be performed as described in the laboratory manual.

Protocol-specific requirements for the inclusion and exclusion of participants are detailed in Section 5.1 and Section 5.2, respectively.

Additional tests may be performed during the study as determined necessary by the investigator or required by local regulations.

Investigators must document their review of each laboratory test result.

**Table 6:** Protocol-Required Safety Laboratory Tests

Laboratory test	Parameters		
Hematology	RBC count platelet count hemoglobin hematocrit	RBC indices: MCV MCH	WBC count with differential: neutrophils eosinophils lymphocytes basophils monocytes
Serum chemistry	ALT AST albumin a BUN bilirubin (total and direct) creatinine	GFR glucose potassium sodium calcium chloride bicarbonate	total protein a creatine kinase HbA1C HDL LDL triglycerides C-reactive protein
Routine urinalysis	
 
Specific gravity
 
pH, glucose, protein, blood, ketones, bilirubin, urobilinogen, nitrite, leukocyte esterase
 
Microscopic examination (if blood or protein is abnormal)
 
Urine protein quantitative analysis (if protein is abnormal)
 
		
Pregnancy testing	Highly sensitive serum hCG pregnancy serum test at screening and urine test at other time points (as needed for WOCBP potential, defined in Section 10.4.1)		
Other tests	
 
SARS-CoV-2 nasopharyngeal swab test (PCR) (if applicable)
 
HBV, HCV, HIV (refer to exclusion criterion 4 and Sections 10.2.1.2, 10.2.1.3, and 10.2.1.4, respectively)
 
Menopausal test (FSH) if applicable (to confirm non-WOCBP status)
 
IgGa (to verify exclusion criterion 11)
 
		

<sup>a This result will be blinded postbaseline.

ALT=alanine aminotransferase; AST=aspartate aminotransferase; BUN=blood urea nitrogen; FSH=follicle-stimulating hormone; GFR=glomerular filtration rate; HbA1C=glycated hemoglobin; HBV=hepatitis B virus; hCG=human chorionic gonadotropin; HCV=hepatitis C virus; HDL=high-density lipoprotein; IgG=immunoglobulin G; LDL=low-density lipoprotein; MCH=mean corpuscular hemoglobin; MCV=mean corpuscular volume; PCR=polymerase chain reaction; RBC=red blood cell; WBC=white blood cell; WOCBP=women of childbearing potential

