## 10.2.1.2. Hepatitis B Virus

Active acute or chronic HBV is exclusionary. Participants with an active acute or chronic HBV at screening will be excluded from the study.

The serologic marker combinations shown in Table 7 will be used to identify an active HBV infection.

**Table 7:** Interpretation of Hepatitis B Serological Test Results

	Test resul	lt	
HBsAg	Anti-HBc	Anti-HBs	Interpretation
Positive	Positive	Negative	An active HBV infection is exclusionary
Negative	Positive	Negative	A low-level chronic HBV infection with impaired liver function is exclusionary a

anti-HBc=total hepatitis B core antibody; anti-HBs=hepatitis B surface antibody; HBsAg=hepatitis B surface antigen; HBV=hepatitis B virus

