## 10.2.1.4. Human Immunodeficiency Virus

HIV-positive is permissible if all of the following conditions are met:

- CD4  $\geq$  200 cells/mm^3 (Table 9, Section 5.2 exclusion criterion 4.d)
- Viral load is < 200 copies/mm³ or undetectable (Table 9, Section 5.2 exclusion criterion 4.c)
- Participant is receiving stable antiretroviral therapy for at least 3 months (minimally) before screening

<sup>a This decision will be made by a medical doctor with sufficient experience in hepatology or infectious disease. Additional tests (eg, HBV viral load) could be required to determine the participant's status.

• AIDS-defining condition is absent

AIDS-defining conditions include the following:

- Cytomegalovirus retinitis with loss of vision
- Pneumocystis jiroveci pneumonia
- Chronic intestinal cryptosporidiosis
- Mycobacterium tuberculosis (pulmonary or extrapulmonary)
- HIV-related encephalopathy
- Invasive cervical cancer

**Table 9:** Interpretation of HIV Test Results

HIV test result	Clinical condition/CD4 count/ viral load	Interpretation
Positive	AIDS-defining condition is present or CD4 < 200 cells/mm 	Test results and clinical conditions or CD4 count confirm the AIDS diagnosis, which is exclusionary
Positive	Viral load > 200 copies /mm³ despite participant receiving antiretroviral therapy	Participant is ineligible because the antiretroviral therapy is not adequate
Positive	Viral load< 200 copies/mm³ but the participant is not receiving antiretroviral therapy	Participant is ineligible because not receiving antiretroviral therapy

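### Exclusion criterion 4a and Table 7 contradict each other on hepatitis B: outright for one serology pattern, and for a second whenever the specialist would exclude

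*Protocol*

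**What the plan says.** Criterion 4a in Protocol Section 5.2 excludes HBV serology that points to acute or chronic infection, "unless associated with a negative HBsAg or negative HBV DNA test". The two exceptions are joined by *or*, so one is sufficient.

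Section 10.2.1.2 (Appendix 2) excludes anyone with active acute or chronic HBV at screening and adds: "The serologic marker combinations shown in Table 7 will be used to identify an active HBV infection". Table 7 has two rows:

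- Row 1, HBsAg positive, anti-HBc positive, anti-HBs negative: "An active HBV infection is exclusionary". It has no footnote and no DNA exception.
- Row 2, HBsAg negative, anti-HBc positive, anti-HBs negative: "A low-level chronic HBV infection with impaired liver function is exclusionary". Footnote a applies to this row only: "This decision will be made by a medical doctor with sufficient experience in hepatology or infectious disease". It continues: "Additional tests (eg, HBV viral load) could be required to determine the participant's status". (In the text as supplied, the footnote is printed within the HIV section that follows.)

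On which text governs, Appendix 2 opens with "Protocol-specific requirements for the inclusion and exclusion of participants are detailed in" Sections 5.1 and 5.2. Table 6 in the same appendix directs the reader, for the viral tests, to both places: "refer to exclusion criterion 4 and Sections 10.2.1.2".

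**The concern.** A site applying criterion 4a and a site applying Table 7 are both following the protocol, yet they can reach opposite decisions on the same screenee. Section 5 bars waivers to the enrollment criteria, so a site cannot settle the matter by asking for an exemption. It needs one rule.

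The rule concerns safety. Section 2.3.1 lists serious infection as one of two potential clinically significant risks, because the drug lowers IgG. The Schedule of Activities has hepatitis serology once, at screening, so the screening decision is the only scheduled point at which HBV status is checked.

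**Working it through.** No arithmetic in the plan bears on this, so the check sets the two rules side by side.

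**Rules used**

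- Criterion 4a: where serology suggests infection, exclude unless HBsAg is negative or HBV DNA is negative.
- Table 7 row 1: exclude.
- Table 7 row 2: exclude if the footnote physician makes the finding described in that row; otherwise do not.

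**Case by case**

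| Screenee | Criterion 4a | Table 7 | Result |
|---|---|---|---|
| Row 1 pattern, DNA positive | Excluded | Excluded | Agree |
| Row 1 pattern, DNA negative | Not excluded (DNA exception) | Excluded | Conflict, always |
| Row 2 pattern, physician makes the finding | Not excluded (HBsAg negative), even if DNA is positive | Excluded | Conflict |
| Row 2 pattern, physician clears | Not excluded | Not excluded | Agree |

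**Does precedence resolve it?**

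- If Section 5.2 prevails, row 2 can never operate. Every row 2 screenee is HBsAg-negative by definition, so 4a would cancel the row and its specialist procedure each time.
- If Table 7 prevails, the DNA exception in 4a has no effect for row 1 and the HBsAg exception has none for row 2.
- Neither text says that it overrides the other.

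**Comparison with hepatitis C.** Criterion 4b and Table 8 both state the exception for a negative RNA test. For HBV, only 4a states a DNA exception.

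**Same check after the proposed change.** Three markers give 2 × 2 × 2 = 8 patterns; with DNA positive or negative, 8 × 2 = 16 combinations. Table 7 covers 2 patterns × 2 = 4 of them and leaves 16 − 4 = 12 unlisted.

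- Main option: in 4a, the 2 row 2 combinations move from exempt to physician decision. In Table 7, 1 combination (row 1, DNA negative) moves from excluded to not excluded.
- Alternative (row 1 excluded whatever the DNA result): 4a changes in 2 + 1 = 3 combinations and Table 7 in none.

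Under either option all 4 Table 7 combinations agree with 4a, and the 12 unlisted ones keep their present result. These counts describe the wording. They say nothing about how often each pattern occurs.

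**The case against.** The strongest reply has three parts.

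**Precedence.** Appendix 2 points to Section 5.2 for the exclusion requirements. On that reading Table 7 only identifies infection and 4a then applies its exceptions, so the row 1 problem is an exception left out of a table. This does not stand as a full answer: it empties row 2 and its footnote of effect, and Table 6 sends sites to both texts. It is a fair guide to the likely intent for row 1, and it supports adding the exception there.

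**Other criteria.** Not being excluded by 4a does not make a person eligible. Criterion 3 covers clinically significant uncontrolled viral infection. Criterion 5 covers clinically significant disease and conditions that the investigator considers an undue risk. A person whom an experienced physician judges to have chronic HBV with a damaged liver would probably be caught by one of these. This stands in large part. It makes the second conflict weaker than the first, though the decision then rests on general judgement instead of on the rule written for HBV.

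**Small safety effect.** The eligibility safeguard named in Section 2.3.1 uses the wording of criterion 3, which is intact on either reading. The row 1 conflict arises only in people with a negative DNA result, and neither the Schedule of Activities nor Table 6 names an HBV DNA test. Chemistry, including ALT, AST and bilirubin, is scheduled at 8 visits through week 24 (screening, baseline, and weeks 4, 8, 12, 16, 20 and 24). Infections are adverse events of special interest, reportable within 24 hours. All of this stands. These measures limit harm; they do not settle eligibility.

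**Conclusion.** Wrong as written, with a minor safety effect and low severity. Criterion 4a and Table 7 conflict unconditionally for one group (row 1 pattern, DNA negative). They conflict conditionally for a second (row 2 pattern, physician would exclude), where criteria 3 and 5 probably recover most cases. That last judgement is an assumption about how investigators would apply those criteria. The documents give no count of screenees affected; with about 30 randomized participants it is probably very small.

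A reader might infer more than this, in three ways that the documents do not support:

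- *That 4a admits people with chronic HBV and liver impairment.* It fails to exclude them, but criteria 3 and 5 still apply.
- *That every isolated anti-HBc screenee is in dispute.* One whom the footnote physician clears passes under both texts.
- *That the trial's results are affected.* Sample size, analysis sets and the primary analysis do not depend on this rule, and no statistical figure changes.

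**What to change.** 1. In criterion 4a, state that the negative-HBsAg exemption does not apply to the HBsAg-negative, anti-HBc-positive, anti-HBs-negative pattern, which is decided under Table 7 row 2 and its footnote. For this pattern a negative DNA result informs the physician's decision and does not exempt by itself.
2. Give row 1 the same rule as 4a by adding *unless HBV DNA is negative*, parallel to Table 8 for hepatitis C. If the sponsor's clinical team prefers to exclude row 1 whatever the DNA result, say so in 4a for that pattern only. Deleting the DNA exception from 4a altogether would go too far: it would also newly exclude DNA-negative people in three HBsAg-positive patterns that Table 7 does not list.
3. Leave all other serology patterns as they are.

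The cost is a text amendment in two places, or in 4a alone under the alternative. No new scheduled test is needed: 4a already names HBV DNA as a ground for exemption, and the footnote already allows viral load for row 2. The downside is possibly a very few fewer eligible screenees.

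### Exclusion criterion 4c bars HIV with CD4 < 200 cells/mm³ only together with an AIDS-defining condition, while Section 10.2.1.4 and Table 9 bar either one alone

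*Protocol*

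**What the plan says.** Two places in the protocol set the rule for HIV-positive participants.

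- **Section 5.2, criterion 4.** Item 4c excludes on a CD4 count below 200 cells/mm³ where the results are ones "that are associated with an AIDS-defining condition". Item 4d excludes on a CD4 count of 200 or more in a participant "not adequately treated with antiviral therapy". Section 5.2 defines neither the AIDS-defining conditions nor adequate treatment, and neither item refers to Section 10.2.1.4.
- **Section 10.2.1.4 (Appendix 2).** "HIV-positive is permissible if all of the following conditions are met": CD4 of at least 200, viral load below 200 copies/mm³ or undetectable, stable antiretroviral therapy for at least 3 months before screening, and no AIDS-defining condition. The first row of Table 9 reads "AIDS-defining condition is present or CD4 < 200 cells/mm", with the interpretation "Test results and clinical conditions or CD4 count confirm the AIDS diagnosis, which is exclusionary".

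The appendix cites criterion 4 for two of its four conditions. The CD4 bullet cites 4.d. The other reads "Viral load is < 200 copies/mm³ or undetectable (Table 9, Section 5.2 exclusion criterion 4.c".

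Table 6 in Section 10.2 links the two places: "HBV, HCV, HIV (refer to exclusion criterion 4 and Sections 10.2.1.2, 10.2.1.3, and 10.2.1.4, respectively". The text introducing that table, however, says that the requirements for including and excluding participants are set out in Sections 5.1 and 5.2.

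**The concern.** Item 4c joins the two features; Table 9 separates them. The same HIV-positive person can pass 4c and 4d and fail Section 10.2.1.4. The rule concerns immunodeficiency in a trial of a drug that lowers IgG. Section 8.4.6 makes infections the adverse event of special interest, and Section 2.3.1 names exclusions in Section 5.2 as a mitigation for serious infection. A site that works from the Section 5.2 list alone could reach the less strict answer. Section 8 requires all eligibility criteria to be confirmed before randomization, and Section 5 allows no waivers, so the list and the appendix should state one rule.

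**Working it through.** The plan gives no figure to reproduce. The check is a logical comparison of the two rules.

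**Inputs.** Four yes/no features, all taken from Section 5.2 and Section 10.2.1.4:

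- L: CD4 below 200
- A: AIDS-defining condition present
- V: viral load below 200 copies/mm³ or undetectable
- S: stable antiretroviral therapy for at least 3 months

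This gives 2⁴ = 16 profiles. Item 4d does not define adequate treatment, so it is read here as Section 10.2.1.4 would have it: T = V and S.

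**Rules.**

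- 4c/4d exclude if (L and A) or (not L and not T).
- Section 10.2.1.4 excludes if L or A or not T.

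| CD4 | AIDS-defining condition | Adequately treated | Profiles | 4c/4d | 10.2.1.4 |
|---|---|---|---|---|---|
| < 200 | yes | either | 4 | excluded (4c) | excluded |
| < 200 | no | either | 4 | **not excluded** | excluded |
| ≥ 200 | yes | no | 3 | excluded (4d) | excluded |
| ≥ 200 | yes | yes | 1 | **not excluded** | excluded |
| ≥ 200 | no | no | 3 | excluded (4d) | excluded |
| ≥ 200 | no | yes | 1 | not excluded | permitted |

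**Result as written.** 4c/4d exclude 4 + 3 + 3 = 10. Section 10.2.1.4 excludes 16 − 1 = 15. The two disagree on 15 − 10 = 5 profiles: 4 with CD4 below 200 and no AIDS-defining condition, and 1 with treated CD4 of 200 or more and such a condition.

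**What other text removes.**

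1. Assume that exclusion 3, "Clinically significant uncontrolled active acute or chronic bacterial, viral, or fungal infection", applies whenever viral load is not controlled. Two of the four low-CD4 profiles have V = no, so 5 − 2 = 3 remain.
2. Assume also that an AIDS-defining condition counts as a prior AIDS diagnosis, which Appendix 8 lists as ruling out pSS classification. That removes the CD4 ≥ 200 profile, so 3 − 1 = 2 remain. Both have CD4 below 200, controlled virus and no AIDS-defining condition, one on stable therapy and one not.
3. If the site also applies Section 10.2.1.4, none remains enrollable.

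**After changing 4c to *or*.** 4c then excludes 4 + 4 + 3 + 1 = 12, and 4d adds the 3 untreated profiles with CD4 ≥ 200 and no AIDS-defining condition: 12 + 3 = 15, with no disagreement. This depends on reading the Section 10.2.1.4 definition into 4d. Without that, consider CD4 ≥ 200, suppressed virus, 2 months of therapy and no AIDS-defining condition. A site could call this adequately treated under 4d, yet Section 10.2.1.4 requires at least 3 months. Full agreement therefore needs the definition tied to 4d as well.

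**Citations.** The viral-load bullet cites 4.c, which says nothing about viral load or treatment; treatment adequacy is in 4.d. The CD4 bullet cites 4.d, which contains the figure of 200 but excludes for inadequate treatment, not for a low count. The two citations look swapped.

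**The case against.** The strongest reply is that the list is incomplete, not contradictory. Section 5.2 names reasons to exclude; it nowhere says that CD4 below 200 without an AIDS-defining condition is acceptable. A site can satisfy both sections by applying the stricter one. It would probably open Section 10.2.1.4 anyway, because the terms in 4c and 4d are explained only there and Table 6 points to it. This largely stands, and it is why the severity is low. It does not remove the mismatch: 4c and 4d carry no pointer of their own, and Section 10.2 also directs readers back to Section 5.2 for eligibility.

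A second reply is that other criteria catch these people: exclusion 3; exclusion 2 for recent invasive cervical cancer, one of the six listed AIDS-defining conditions; Appendix 8; and investigator judgment under exclusions 1 and 5. This holds for most cases. Exclusion 3 does not clearly reach a participant with suppressed virus, and Appendix 8 turns on a prior diagnosis, so it does not clearly reach a low count first found at screening.

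A third reply is that CD4 below 200 is itself AIDS-defining, as the Table 9 interpretation suggests. A low count is not among the six conditions listed in Section 10.2.1.4. That reading would make the qualifier in 4c redundant, and it still leaves out an AIDS-defining condition with CD4 of 200 or more.

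A reader might also infer that the protocol opens the trial to severely immunodeficient participants. It does not: Section 10.2.1.4 bars every such profile. Nor does the no-waiver rule show a conflict; if anything it favors holding sites to the stricter text.

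**Conclusion.** The point holds: 4c is wrong as written, at low severity. Taken alone, 4c and 4d do not exclude CD4 below 200 without an AIDS-defining condition, or adequately treated CD4 of 200 or more with one; Section 10.2.1.4 and Table 9 exclude both. The clearest case left uncovered by other criteria is a virally suppressed participant on stable therapy with CD4 below 200, no AIDS-defining condition and no prior AIDS diagnosis.

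The figure of 5 in 16 counts logical profiles and is not a rate. Merging viral load and therapy into one feature gives 3 of 8 instead. The later counts rest on the stated readings of exclusion 3, Appendix 8 and 4d. The documents give no HIV prevalence; with approximately 30 participants and the other safeguards, few if any are likely to be affected. Sample size and analysis are unchanged.

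**What to change.** 1. Reword 4c to: *HIV with a CD4 count < 200 cells/mm³ or an AIDS-defining condition (see Section 10.2.1.4)*. This adopts the rule that Section 10.2.1.4 already states twice, in its list of conditions and in Table 9, so it needs no new clinical decision.
2. Add to 4d that adequate treatment is as defined in Section 10.2.1.4: viral load < 200 copies/mm³ or undetectable, on stable antiretroviral therapy for at least 3 months. This is needed for the two sections to agree in full.
3. In Section 10.2.1.4, swap the two citations so that the CD4 bullet cites 4.c and the viral-load bullet cites 4.d.

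The cost is two edited criteria and two corrected citations. Procedures, sample size and analysis stay as they are.
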